Hypothesis. In the YELLOW III study, we hypothesize that LDL-C lowering with evolocumab 140 mg every 2 weeks will result in a significant increase in OCT-defined minimal FCT and reduction of plaque lipid content assessed by NIRS compared to baseline in patients with CAD undergoing percutaneous coronary intervention (PCI). In addition, we hypothesize that there is an association between the changes in patient's plaque characteristics and PBMC gene expression and lipid metabolites at the baseline, which would allow us to develop a predictive model for detecting subjects that demonstrate the greatest response regarding plaque morphology to PCSK9 inhibition therapy. YELLOW III will provide an additional contribution to the ongoing HYUGENS study due to its unique design combining intravascular imaging and transcriptomic based machine learning approach, which will allow to uncover molecular mechanisms responsible for the beneficial changes in atherosclerotic lesions of patients treated with evolocumab.

STUDY OBJECTIVES

The aim of the study is to assess the effect of evolocumab on coronary plaque morphology using intravascular imaging, NIRS/IVUS and OCT, and PBMC gene expression analysis in patients with stable CAD on maximally tolerated statin therapy.

Primary endpoints. The primary end-points are the changes from baseline to follow-up (follow-up value minus baseline value) in (1) the minimal FCT assessed by OCT and (2) NIRS maxLCBI4mm after 26 weeks of evolocumab.

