Secondary endpoints. The secondary endpoints are the changes in (1) the maximal lipid arc, lipid length, lipid volume index, macrophage accumulation and calcification by OCT; (2) PAV and TAV defined by IVUS and (3) PBMC gene expression. In recognition of the role of lipids in CAD and atherosclerosis, we will perform lipidomics to analyze lipid metabolites and lipid derivatives in blood plasma and serum in order to identify CAD biomarkers. Measuring lipid metabolites (and their effectors) might directly lead to the identification pathways of lipid action or lipid metabolism in patients receiving treatment. We will also perform Mass Cytometry (CyTOF) of PBMC to characterize the immune profile and responses in patients receiving a combination of evolocumab plus statin with an eye on identifying biomarkers for detecting and/or predicting favorable changes in plaque morphology as a result of PCSK9 inhibition therapy. Other parameters including the levels of CRP, resistin, adiponectin, perilipin and Lp(a) will also be measured for the same purpose.

Exploratory endpoints. Major Adverse Cardiac Events (MACE) will be defined as a combined clinical endpoint of death, MI (Q wave or non Q-wave with CK-MB >3 times above the upper normal limit (48 U/L), urgent revascularization or stroke at 30 days and 1 year.

STUDY PROCEDURES

This is a single center single arm study, which will be performed in the Cardiac Catheterization laboratory of the Mount Sinai Hospital, New York, NY. After informed consent, patients undergoing clinically indicated elective PCI with a non-obstructive lesion and optimal background statin therapy will be eligible for screening (Figure 1). Non-obstructive lesions (30-50% stenosis) identified by angiography in a non-culprit vessel with lipid-rich plaque will be studied. Subjects will receive evolocumab 140 mg subcutaneously every 2 weeks for 26 weeks. Serial NIRS/IVUS and OCT imaging will be performed in the non- obstructive lesions, first during PCI and subsequently after 26 weeks.

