 Screening. Written informed consent must be obtained from all subjects before any study-specific procedures are performed. We will screen patients scheduled for elective coronary angiography and/or coronary artery stenting, who are receiving statin therapy for at least 4 weeks or with history of statin intolerance (should not exceed 20% of the total cohort) with acceptable LDL-C levels. Patients with nonobstructive lesion (30-50% stenosis) by angiography and lipid-rich plaque with lipid arc >90° and minimal fibrous cap thickness ≤ 120 µm detected by OCT will comprise the final study population. Women of childbearing potential will undergo urine pregnancy testing. If necessary, we may request serum pregnancy testing to confirm equivocal urine-based results.

- 2. PCI and baseline imaging. Culprit vessel PCI will be performed according to best current practice. During the same angiographic procedure baseline OCT and NIRS/IVUS imaging of the non-obstructive study lesion will be performed after administration of intra-coronary NTG. A total of 25ml of blood will be drawn from the sheath during angiography for transcriptomic profiling of PBMC (mRNA and miRNA), lipidomics and cytokine analyses. Patients will undergo assessment of lipid levels, CK-MB, Troponin I, liver function, CBC, and hsCRP.
- 3. **Study drug allocation.** All patients will receive subcutaneously administered evolocumab 140 mg every 2 weeks for 26 weeks in addition to statins. Evolocumab will be administered on day 1 (the day of the first treatment) and through week 26 with a personal injector or prefilled auto injector/pens.
- Clinical visits. Study visits will occur during screening (day 1), weeks 12 and 26 (time of follow-up procedure). Subjects must fast overnight when fasting lipid samples are to be obtained.
- 5. Follow up Procedure. The follow-up procedure will be scheduled 26 weeks after the baseline PCI and should occur within ±2 weeks of their specified date. First, routine angiography to check the previous stent will be performed, then, repeat NIRS/IVUS and OCT of the non-obstructive study lesion will be performed after administration of intra-coronary nitroglycerin. A total of 25ml of blood will be drawn

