from the sheath during angiography for transcriptomic profiling of PBMC (mRNA and miRNA), lipidomics and cytokine analyses.. All study patients will undergo repeat assessment of lipid levels, CK-MB, Troponin I, liver function, CBC, and hsCRP. Bivalirudin or Heparin will be used as anticoagulation as per standard PCI protocol. All patients will have repeat CK-MB and TnI levels measured at 6-8 hours and if in hospital, 16-24 hours post PCI, and thereafter if levels continue to rise

- 6. Post Follow-up. After the follow up procedure patients will be referred back to their primary care physician as is our usual practice. All further adjustment of lipid lowering and other medications will be at the discretion of the primary care physician. The treatment received after 26 weeks of evolocumab will be documented, and clinical telephone follow up will be performed at 30 days, 6 months and 1 year after the follow-up procedure
- 7. Data analysis. Off-line image analysis will be performed by the Mount Sinai Intravascular Imaging core laboratory, which will have no knowledge of patient clinical presentation and treatment.. Statistical and bioinformatics analyses will be performed by an independent biostatistician unaware of clinical data.

For predictive model construction, each patient will be identified as an evolocumab responder or non-responder depending on whether FCT increased or decreased after the treatment. Similar to our YELLOW II transcriptomic sub study (23), an elastic net regularized generalized linear model and K top scoring pair (KTSP) classifier model will be built using clinical variables and PBMC transcriptomic, lipidomics and cytokine analyses data to predict changes in FCT to ascertain whether a patient's FCT will increase in response to treatment. The transcriptomic data will be pre-processed to identify the

mechanism of missing data, and data imputations will be performed for non-ignorable missing data. The accuracy, sensitivity and specificity of both algorithms will be evaluated in order to select the highest performing model. We believe that the predictive model might allow patients to have their FCT response approximated without undergoing intravascular imaging.

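### Core-laboratory masking does not state that readers are blind to which scan is baseline and which is week 26, although the primary endpoints are uncontrolled before-after changes

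*Combined protocol and SAP*

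**What the plan says.** The only statement on masking of image readers is in Study procedures, item 7 (Data analysis): the core laboratory is one "which will have no knowledge of patient clinical presentation and treatment". The same item says the biostatistician is independent and unaware of clinical data.

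The rest of the design sets what that masking has to achieve:

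- Study procedures, opening paragraph: "This is a single center single arm study". Imaging of the study lesion takes place "first during PCI and subsequently after 26 weeks".
- Study procedures, item 3: "All patients will receive subcutaneously administered evolocumab 140 mg every 2 weeks for 26 weeks in addition to statins".
- Study objectives, Primary endpoints: the changes, follow-up minus baseline, in OCT minimal FCT and in NIRS maxLCBI4mm.
- Hypothesis: evolocumab "will result in a significant increase in OCT-defined minimal FCT", together with a fall in plaque lipid content.
- Screening: patients whose lesion meets the lipid-arc and cap-thickness limits "detected by OCT will comprise the final study population". The baseline scan is therefore also the eligibility scan. The text does not say who makes that eligibility reading.
- Item 7 again: responder status is assigned "depending on whether FCT increased or decreased after the treatment".

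Nothing in the text reviewed mentions removal of scan date or visit, order of reading, or masking to baseline versus week 26.

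**The concern.** In a randomised trial, masking readers to treatment hides the comparison being made. Here there is no second arm. The contrast under test is before versus after, so masking to 'treatment' protects the primary comparison only if it means masking to timepoint. The word could also mean background statin therapy, which does vary between patients (Screening; Inclusion criteria) but is not what the endpoints compare. On that narrower reading, a laboratory could read each dated scan as it arrived, know its timepoint, and still follow the plan.

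If knowledge of timepoint shifts the readings, no control group cancels the shift. It passes straight into the mean change in minimal FCT and into the reader-measured OCT and IVUS secondary endpoints. It also reaches the responder label: because that label depends only on the sign of the FCT change, a small shift can reclassify patients whose change is near zero, and the predictive model is trained on the result. The hypothesis is directional, so an expectation effect would favour it. A masked statistician cannot correct values already recorded.

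**Working it through.** **Step 1. What the text masks, and what needs masking.**

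- Assigned drug: the same for everyone (item 3), so there is nothing to hide between patients.
- Background statin: varies, but is not the comparison made by the primary endpoints.
- Timepoint: is the comparison made by the primary endpoints, and is not named in item 7.

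The gap is therefore in the specification. The text does not show that readers know the order.

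**Step 2. Illustration of size.** There is no figure in the plan to reproduce. The text reviewed gives no SD of FCT change, alpha, primary test or planned sample size. Inputs:

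- n = 110 pairs. This is the last numbered DSMB meeting count (item 8, Safety reporting), not a sample size.
- SD of change 40, 50 or 60 µm (assumed).
- True mean change 0; mean reading shift 5 µm toward thicker caps at follow-up (both assumed).
- Two-sided 5% test, counting only significant increases (assumed).

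SE = SD/√110. Chance of a false significant increase = 1 − Φ(1.96 − shift/SE). With zero shift this is 2.5%.

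| SD (µm) | SE (µm) | 5/SE | Chance of false increase | Shift giving 50% (1.96 × SE) |
|---|---|---|---|---|
| 40 | 3.81 | 1.31 | 25.8% | 7.5 µm |
| 50 | 4.77 | 1.05 | 18.1% | 9.3 µm |
| 60 | 5.72 | 0.87 | 13.9% | 11.2 µm |

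**Step 3. Cross-check and dependence on n.** A shift of 5 µm with SD 50 is 0.10 SD. A paired t-test has noncentrality 0.10 × √n. From the noncentral t distribution, the chance of a false significant increase is 7.6% at n = 30, 12.8% at n = 70 and 17.9% at n = 110. The last agrees with the normal approximation in the table. For a fixed shift, more patients make the false positive more likely.

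**Step 4. How well masking could work.** Entry requires FCT of 120 µm or less (Screening; Inclusion criteria, OCT criteria), so a thicker cap hints at a follow-up scan. With an assumed follow-up SD of 40 µm, the share of follow-up scans above 120 is 1 − Φ((120 − mean)/40): 15.9%, 30.9%, 50.0% and 69.1% at assumed follow-up means of 80, 100, 120 and 140 µm. This is a hint and not proof of order, because a re-read baseline can also exceed 120.

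**The case against.** The strongest reply is that the plan already covers the point. In a single-arm trial where all patients take the drug, the natural meaning of masking to treatment is masking to pre- or post-treatment status. A reader who knew a scan was from week 26 would know the patient was on evolocumab, which would breach item 7. What remains would then be the ambiguity of one word. That reading is reasonable and may be what was intended. It is not written down, however, and the text gives no procedure (date removal, reading order, locking) that would put it into effect.

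Other points stand as limits:

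- An imaging manual or core-laboratory procedure outside the text reviewed may deal with timepoint. Confidence is high only that the plan does not state it.
- The shift, the SDs and the zero true change in the illustration are assumed, and n is borrowed from a DSMB milestone. Varying n as well as SD widens the range beyond 14-26%.
- One of the two primary endpoints, maxLCBI4mm, is a calculated index (Background) and is less exposed than minimal FCT.
- Masking would not supply a control group, nor remove regression to the mean from selecting lesions on baseline FCT. That is a separate matter.

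**Conclusion.** The concern holds as a gap in the specification: the plan does not clearly hide scan order from the readers, and scan order is the contrast that the primary endpoints measure. It should be fixed. It is not evidence that a bias exists.

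The main exposure is minimal FCT, the reader-measured OCT and IVUS secondary endpoints, and the responder label. Under the stated assumptions, a mean shift of 5 µm takes the chance of a false significant increase in FCT from 2.5% to about 14-26%, and a shift of 7.5-11.2 µm takes it to 50%. These figures show how sensitive an uncontrolled before-after test is to a small systematic reading shift. They do not estimate its size in this laboratory.

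**What to change.** Replace the masking sentence in Study procedures, item 7, with wording such as:

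> Core-laboratory readers will be masked to clinical presentation, treatment and imaging timepoint. Each patient's two pullbacks will be stripped of date and visit, matched for segment and read in random order. Both readings will be locked before the order is disclosed. The endpoint baseline is this masked off-line reading and not the eligibility reading.

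If 'treatment' was already meant as before/after status, this only makes it explicit. The last sentence is needed because whoever makes the eligibility reading knows that the scan is the baseline one.

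The cost is small: amended text, removal of labels, and reading each pair together by existing readers, with no new patient procedures. If the core laboratory also makes the eligibility reading (not stated), one repeat baseline reading per patient is added.

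There are two drawbacks. Endpoint baseline values will not be available until the week 26 scan is in. Masking will also be imperfect, because a cap thicker than the entry limit suggests follow-up, and does so more often the larger the true increase.

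### The prediction model is trained and selected only on whether FCT rose or fell, so it does not address the strongest-responder aim stated in the hypothesis

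*Combined protocol and SAP*

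**What the plan says.** The Hypothesis section wants a predictive model for "detecting subjects that demonstrate the greatest response regarding plaque morphology to PCSK9 inhibition therapy". Study Procedures, item 7 (Data analysis), gives the operational version: "each patient will be identified as an evolocumab responder or non-responder depending on whether FCT increased or decreased after the treatment". An elastic net generalised linear model and a KTSP classifier are then built from clinical, transcriptomic, lipidomic and cytokine data "to predict changes in FCT to ascertain whether a patient's FCT will increase in response to treatment". On selection: "The accuracy, sensitivity and specificity of both algorithms will be evaluated in order to select the highest performing model". On use, the authors hope that "the predictive model might allow patients to have their FCT response approximated without undergoing intravascular imaging".

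Three other statements bear on this:

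- Under Primary endpoints, minimal FCT is analysed on its continuous scale: "The primary end-points are the changes from baseline to follow-up (follow-up value minus baseline value").
- The design has no control group: "This is a single center single arm study".
- The Screening item says that patients with a 30 to 50% stenosis and a lipid-rich plaque with minimal FCT of 120 µm or less "detected by OCT will comprise the final study population".

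The text reviewed contains no size threshold, no quantile and no continuous model linking the item 7 label to the hypothesis. It does not say which class an unchanged FCT takes.

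**The concern.** Item 7 is consistent in itself: a binary label, classifiers and binary performance measures. The mismatch is with what the model is for. A patient whose cap thickens by a trivial amount and one whose cap thickens most carry the same label, so the models are rewarded for separating small rises from small falls. Nothing in training or selection rewards finding the patients who gain most.

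The hope of approximating FCT response without imaging has the same gap, because a yes/no output gives direction but not size. The size is already available at no extra measurement cost.

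At stake is whether the prediction aim can answer its own hypothesis. The tests of the two co-primary endpoints do not use the label.

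**Working it through.** **Plan's own figure.** None exists to reproduce. The text reviewed gives no expected responder share, no SD or distribution for the FCT change, and no performance target for this model. The inputs below are assumptions unless a section is named.

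**Step 1: is the target really binary?** The phrase about predicting changes in FCT, and the choice of a generalised linear model, could suggest a continuous outcome. But the same sentence ends in whether FCT will increase, KTSP is a classifier, and all three selection measures need classes. As written, the target is the sign.

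**Step 2: how far is the label from the strongest responders?** Let p be the share of patients whose FCT rises, and take the strongest responders to be the top quarter of changes. For p of at least 0.25, everyone in the top quarter is a labelled responder. The share of labelled responders outside it is 1 − 0.25/p, whatever the distribution.

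| p (assumed) | 1 − 0.25/p | Outside top quarter |
|---|---|---|
| 0.5 | 1 − 0.500 | 50% |
| 0.7 | 1 − 0.357 | 64% |
| 0.8 | 1 − 0.313 | 69% |
| 0.9 | 1 − 0.278 | 72% |

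**Step 3: how much information does the sign keep?** For a normally distributed change split at p, the efficiency relative to the continuous value is φ(z_p)² / [p(1 − p)].

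- p = 0.5: 0.3989² / 0.25 = 0.637
- p = 0.7: 0.3477² / 0.21 = 0.576
- p = 0.8: 0.2800² / 0.16 = 0.490
- p = 0.9: 0.1755² / 0.09 = 0.342

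**Step 4: does that depend on normality?** Yes. For a median split and a location shift, the efficiency relative to least squares is 4 f(0)² σ². For t distributions:

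- 5 df: 4 × 0.3796² × 1.667 = 0.96
- 4 df: 4 × 0.3750² × 2 = 1.13
- 3 df: 4 × 0.3676² × 3 = 1.62

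With heavy tails the loss can vanish or reverse.

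**Step 5: does the choice of outcome change regression to the mean?** Suppose there is no drug effect. Assume an unselected FCT mean of 100, 120 or 150 µm, an SD of 30, 40 or 50 µm, and independent reading error with SD 10, 15 or 20 µm at both visits. Keep patients whose baseline reading is above 0 and at most 120 µm (the ceiling is from the Screening item), and let the qualifying reading be the analysed baseline. By simulation over these cells, baseline FCT alone predicts:

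- the sign, with AUC 0.53 to 0.63
- the top quarter of change, with AUC 0.53 to 0.64
- the continuous change, with absolute correlation 0.07 to 0.28

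Selection makes baseline FCT predictive for either outcome, to about the same degree.

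**The case against.** The strongest defence has three parts.

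**The binary target is a deliberate choice.** Item 7 follows the earlier YELLOW II transcriptomic work, whose model also predicted whether FCT increased, and KTSP needs classes. This stands, and it is why the classifiers should remain. It explains the label but does not reconcile it with the hypothesis. The elastic net's fitted probability could be used to rank patients, but the plan neither proposes this nor assesses it.

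**The hypothesis sentence is broad.** The Secondary endpoints section speaks more loosely of predicting favourable plaque changes, which a sign label fits. Rewording the Hypothesis section would therefore remove the contradiction without a new analysis. That is true, but the hope of approximating FCT response would still be unmet and the measured size unused.

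**The sizes rest on assumptions.** They do. The responder share, the top-quarter definition and the normal model are ours. The mismatch in the text needs none of them.

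A reader might also draw stronger conclusions that the documents do not support:

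- **That regression to the mean is a flaw of the sign label.** It arises from selecting on a thin cap in a single arm, and it affects the continuous change as much (Step 5). Changing the outcome does not remove it; only a benchmark makes it visible.
- **That 36 to 42% of the information is simply lost.** This holds only under normality (Step 4).
- **That the planned classifiers are wrong and should be demoted.** That would be preference. They answer the question of direction.

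**Conclusion.** The point holds as a worthwhile, inexpensive improvement, not as an error that threatens the trial. The model as specified predicts direction, while the hypothesis asks for the strongest responders and item 7 hopes to approximate the response.

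If the strongest responders are the top quarter, half to nearly two thirds of labelled responders (50% at an even split, 64% at 70/30) are not among them. Under a normal model the sign keeps about 64% or 58% of the information in the change. That second figure is the less secure of the two, since the documents give no distribution. The argument that size is already measured assumes that FCT in item 7 means minimal FCT, which is plausible but not stated there.

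It would be wrong to infer that the primary results are compromised: the co-primary endpoints are continuous changes and do not use the label.

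**What to change.** In item 7:

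1. Keep the elastic net and KTSP classifiers and their comparison on accuracy, sensitivity and specificity. State which class an unchanged FCT takes, and confirm that FCT means minimal FCT.
2. Add a pre-specified elastic net on the continuous change in minimal FCT, with the same clinical and blood predictors, and use it for the strongest-responder aim in the hypothesis.
3. Report its out-of-sample correlation with the observed change, and its AUC for the sign beside the classifiers. This also shows whether using the size helps to predict direction in these data.
4. Report all models, binary and continuous, against a benchmark that uses baseline FCT alone, so that prediction arising from regression to the mean can be seen.
5. Describe the result as prognostic under evolocumab. Without a control arm it cannot show who benefits because of the drug.

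The cost is about one paragraph and some analysis code. No new patient data or core-laboratory reading is needed. The downsides are one more analysis to specify and the sensitivity of a continuous outcome to outlying changes.

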addition of evolocumab in patients treated with moderate or high intensity statin therapy resulted in greater decrease in percent atheroma volume (PAV) assessed by intravascular ultrasound (IVUS) during 18 month of therapy (12), while there was no plaque regression observed in patients treated with statins alone. Reduction in the atherosclerotic disease burden, atheroma (PAV) was observed in 67% of the evolocumab and 47% of the placebo group regardless of baseline LDL-C levels.

One-third of the patients treated with evolocumab and almost half of statin-treated patients from the GLAGOV trial did not demonstrate plaque volume reduction despite the significant lipid reduction suggesting that different mechanisms might be responsible for lesion regression in a subgroup of patients, and these patients might require different treatment approach. Another possibility is that beneficial changes in lesion morphology were not captured in the study due to inherent limitations of IVUS. Optical coherence tomography (OCT) provides high-resolution (10-20 µm) in vivo images of plaque morphology and is the only currently available intravascular imaging modality capable of the assessment of the fibrous cap thickness in vivo (13,14). The presence of a thin fibrous cap overlying a large necrotic core is the hallmark of high-risk vulnerable plaques (14,15). While intravascular ultrasound (IVUS) lacks the spatial resolution to accurately access the changes in fibrous cap thickness (FCT), OCT's superior image resolution allows the accurate detection of thin cap fibroatheroma (TCFA) and estimate the effect of various lipid-lowering therapies on FCT (16-18). The aim of the ongoing HUYGENS study is to evaluate the effect of evolocumab combined with maximally tolerated statin therapy on

OCT defined FCT in subjects with non-ST-elevation acute coronary syndrome (NSTE-ACS).

Near-infrared spectroscopy (NIRS) detects the lipid (cholesterol) content of atherosclerotic plaques by generating lesion "chemogram" and calculating lipid core burden index (LCBI) characterizing the amount of lipid on a 0 to 1000 scale. Large lipid-core plaques (LCP) detected by NIRS have been shown to be a signature of plaques causing STEMI and are associated with a high risk of periprocedural MI (19,20).

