In our subsequent YELLOW II study, all patients with obstructive NTL received high-dose statin therapy for 8-12 weeks (22). The aim of the study was to characterize the relationship between the changes in plaque morphology assessed by NIRS/IVUS and OCT, HDL functionality and gene expression in peripheral blood mononuclear cells (PBMC) using microarray analysis. At the follow-up, we observed a significant increase in fibrous cap thickness (FCT) in the study lesion, enhancement of cholesterol efflux capacity (CEC) and significant perturbations of PBMC transcriptome in patients with stable coronary artery disease (CAD) treated with 40 mg rosuvastatin for 8-12 weeks. As a result, the prevalence of TCFA reduced from 20 to 7% (P=0.003) and there was a significant independent association between the thickening of the fibrous cap and improved CEC independent of lipid lowering and CRP reduction. In addition, we observed significant transcriptomic perturbations in genes related to cholesterol synthesis, regulation of fatty acid unsaturation, cellular cholesterol uptake, efflux and inflammation suggesting that several independent molecular mechanisms might be responsible for the beneficial effects of statin on plaque morphology. The unique translational combination of multi-modality intravascular imaging with clinically relevant cellular biology and comprehensive transcriptomics represents a powerful approach to assessing the effects and mechanisms of the efficacy of different lipid-lowering therapies for stabilizing atherosclerotic plaques.

With OCT imaging, we observed an increase in FCT after intensive statin therapy only in a subset of the study patients. Traditionally, response to statins is measured by the changes in serum lipids, however, these changes do not predict the beneficial changes in FCT, therefore, it is important to distinguish statin responders from non-responders using non-invasive methods. In our recent analysis, YELLOW II transcriptomic data was used to predict whether a patient's FCT increased in response to statin therapy using machine learning models (23). One of the model used 18 genes and was able identify statin responders with an accuracy of 95.7%, sensitivity of 94.3% and specificity of 97.1%.

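### A rise in FCT is labelled as response to evolocumab in a single-arm study on background statin; the prediction model can support a claim about the combined regimen only

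*Combined protocol and SAP*

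**What the plan says.** Study Procedures describes the design plainly: "This is a single center single arm study". Item 3 (Study drug allocation) adds: "All patients will receive subcutaneously administered evolocumab 140 mg every 2 weeks for 26 weeks in addition to statins". The Screening paragraph accepts patients after at least 4 weeks of statin and allows up to 20% of the cohort to be statin intolerant. It also requires a minimal FCT of 120 µm or less on baseline OCT.

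Item 7 (Data analysis) defines the label for the prediction models: "each patient will be identified as an evolocumab responder or non-responder depending on whether FCT increased or decreased after the treatment". An elastic net model and a K top scoring pair classifier are then trained on it, using clinical, transcriptomic, lipidomic and cytokine data. They are judged by accuracy, sensitivity and specificity.

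The Hypothesis paragraph states the purpose: to "develop a predictive model for detecting subjects that demonstrate the greatest response regarding plaque morphology to PCSK9 inhibition therapy". The Secondary endpoints paragraph likewise seeks biomarkers of favourable plaque change and presents that change as the consequence of PCSK9 inhibition.

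**The concern.** The label names a cause, but it is built from a before-after change in patients who all receive the drug. Any rise in FCT counts, whether it comes from evolocumab, from continuing statin treatment, from the natural course of the plaque, from measurement error or from selection on a thin cap. The text available describes no concurrent or external comparison for the label and no check for a background signature. Accuracy, sensitivity and specificity show how well the label is predicted. They say nothing about what caused it.

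At stake is the meaning of the model. A classifier that finds patients whose caps thicken under any lipid-lowering treatment would perform well here and would be reported as detecting PCSK9-inhibitor response. A reader could then take a prognostic signature as grounds for choosing patients for the drug.

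**Working it through.** The plan states no responder rate or sample size for the model, so there is no figure of its own to reproduce. The check sets the label against what the protocol reports elsewhere.

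**1. FCT rises without evolocumab.** Results of YELLOW I and II reports a significant FCT increase over 8-12 weeks of rosuvastatin 40 mg, confined to a subset of patients, and an 18-gene model that predicted the increase. Item 7 says that the new models will be built in a similar way. Patients may enter YELLOW III after only 4 weeks of statin, so statin-related thickening may still be under way at baseline.

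**2. How common the label was in YELLOW II.** Inputs: accuracy 95.7%, sensitivity 94.3%, specificity 97.1%. With p the share labelled as responders:

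- accuracy = p × sensitivity + (1 − p) × specificity
- p = (0.971 − 0.957) / (0.971 − 0.943) = 0.014 / 0.028 = 0.50
- rounding of the three inputs gives 0.46 to 0.54
- whole-number matches: 35 responders of 70 (33/35, 34/35, 67/70) or 35 of 69 (33/35, 33/34, 66/69)

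This holds only if the three figures come from one unweighted evaluation set. The documents do not say how that set was formed. A balanced set or a median split would give the same result, so 50% is not established as a natural rate on statin.

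**3. A sign-of-change label in a randomised comparison.** The background section reports for the randomised evolocumab IVUS trial: "Reduction in the atherosclerotic disease burden, atheroma (PAV) was observed in 67% of the evolocumab and 47% of the placebo group". The same paragraph says that no plaque regression was seen on statins alone. A label based on direction of change can thus mark nearly half of a group in which no regression is reported.

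- If evolocumab never turns a would-be responder into a non-responder, the share of responders on drug who would have responded anyway is 47/67 = 70%.
- Without that assumption, the two rates allow anything from (67 + 47 − 100)/67 = 14/67 = 21% up to 70%.

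So individual response to the drug is not identified even with a control arm. These figures concern PAV by IVUS over 18 months, not FCT by OCT over 26 weeks.

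**4. Selection on a thin cap.** Patients enter on a low measured value of the outcome. Under assumed values that the documents do not give (true FCT normal with mean 100-150 µm and SD 30-50 µm, measurement SD 10-30 µm, baseline kept if above 20 and at most 120 µm), a simulation with no change in true FCT labelled 52% to 76% of patients as responders. Without the entry rule the share would be 50%. Only the direction should be taken from this; the size depends on the assumptions.

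**The case against.** The strongest reply is that the model is meant only to predict FCT change in patients given this regimen. Item 7 ends by hoping to approximate FCT response without intravascular imaging, and that use needs prediction, not attribution. The single-arm design is stated openly. The model is an additional item under Hypothesis, not a listed endpoint, and the primary endpoints do not depend on it. All of this stands, and the predictive use survives the fix. It does not rescue the label or the Hypothesis and Secondary endpoints wording, which name PCSK9 inhibition as the cause.

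A second reply is that the background figures do not transfer. This also stands. YELLOW II studied obstructive lesions on high-dose statin for 8-12 weeks. YELLOW III studies 30-50% lesions in patients already on statin or intolerant of it, and the PAV rates come from another modality and duration. The documents themselves say that IVUS cannot resolve changes in FCT accurately.

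A reader might infer three stronger things that the documents do not support:

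- *That 70% of responders here, or half of all patients, would have thickened without evolocumab.* The first is an analogy and the second depends on an unknown evaluation set.
- *That the new model will merely relearn the statin signature.* This is possible, but the population differs and the new models add clinical, lipidomic and cytokine data.
- *That a signature which adds to the YELLOW II score is specific to evolocumab.* Without a control, it could add because of population, lesion type, duration, extra data types, regression to the mean or overfitting. Nor would failure to add exclude a drug effect.

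**Conclusion.** The concern holds as a mismatch between claim and design. In this study an FCT rise cannot be attributed to evolocumab in an individual patient, and a classifier with high accuracy may be purely prognostic. The conclusion rests on the single-arm design, the background statin, the reported FCT rise on statin alone and the entry rule. It needs none of the illustrative percentages. The share of labelled responders who owe the rise to evolocumab cannot be computed from the documents. The point is worth correcting before analysis because it decides what the prediction work may conclude. It does not alter the definition of the primary endpoints and is not a demand for a control arm.

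**What to change.** **Wording and claim.** In Hypothesis, Secondary endpoints and item 7 (Data analysis), replace the evolocumab-responder label, and the phrases that present plaque change as response to or consequence of PCSK9 inhibition, with *FCT increase (or plaque change) during evolocumab plus background therapy (statin where tolerated)*. State that the model predicts this outcome under the combined regimen, and that no claim of evolocumab-specific response or of selecting patients for the drug will be made from it.

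**Optional descriptive check.** If the YELLOW II 18-gene model is available and maps to the expression platform, apply it unchanged to the YELLOW III baseline data. Report its discrimination for FCT increase beside the new model's out-of-sample performance. Good discrimination by the older model would warn of a shared signature. Specify in advance that incremental value over it will not be read as evidence of evolocumab specificity.

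**Cost.** Edits in three places, a less ambitious claim and, if the check is done, a small extra analysis on baseline samples already planned, with some work to map genes between platforms.
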